## CLINICAL TRIAL PROTOCOL SYNOPSIS

Name of company:		Tabulated	
Boehringer Ingelheim		Trial Protocol	
Name of finished produ	ıct:	-	
•			
Not applicable		4	
Name of active ingredie	ent:		
BI 836826			
Protocol date: 27 Jul 2010	Trial number: 1270.1		Revision date: 04 Mar 2015
Title of trial:	A Phase I, open, dose es chronic lymphocytic leu	ccalation trial with BI 836826 in pati kaemia	ents with advanced
Coordinating Investigator:			
Trial site(s) :	Multi-center trial		
Clinical phase:	Phase I		
Objective(s):		num tolerated dose (MTD), safety a fficacy of BI 836826 monotherapy in (CLL).	
Methodology:	Open-label dose escalati	ion	
No. of patients:	About 70		
total entered:	About 60		
Diagnosis :	Chronic lymphocytic leu	ukaemia (CLL)	
Main criteria for inclusion:	Adult patients with activ regimens	ve CLL who have received at least to	wo prior treatment
Test product(s) :	BI 836826		
dose:	The starting dose for BI	836826 will be 1 mg.	
mode of admin. :	BI 836826 administered course.	intravenously as one to three single	doses within a 14 day
Comparator products:	Not applicable.		
dose:			
mode of admin. :			
Duration of treatment:	5	v treatment course. Patients are eligil or investigator requests treatment di	1

Page 3 of 111

Name of company: Boehringer Ingelheim		Tabulated Trial Protocol	
Name of finished prod	luct:	-	
Not applicable			
Name of active ingred	ient:		
BI 836826			
Protocol date: 27 Jul 2010	Trial number: 1270.1		Revision date: 04 Mar 2015
Criteria for efficacy, pharmacokinetics, pharmacodynamics:	Number of lymphocytes overall response, progres	in the peripheral blood, ssion free survival, failure free surv	, blood counts, best ival,
Criteria for safety:	Maximum tolerated dose, incidence and intensity of adverse events graded according to the common terminology criteria for adverse events (CTCAE, version 4.0), incidence of dose limiting toxicity, laboratory parameters.		
Statistical methods:	Descriptive statistics.		

Page 4 of 111

## **FLOW CHARTS**

Trial Periods	Screen		7	Treat	ment**		EOT/FU
Course *		1		-	If no signs o		
Visit *	Screen	1	-		2	3	progression
Days	-14 to -	1	2	3	4	8	please
	1						continue to
Informed consent	X						Visit 1 Flow
Demographics	X						Chart
Medical history	X						Course 2-8
Review of in-/exclusion criteria	X	X					Tf the method
12 lead-ECG	x						
 
If the patien
 
has disease
 

							progression
	-						or
Height	X						withdraws,
Physical examination,	X	X					please
							continue to
ECOG performance status							EOT visit or
Vital signs	X	X	x	x	X	x	Flow Chart
Weight	X	X					Course 2-8
Dose assignment	x 						
Adverse events		X	X	X	X	х	
Concomitant therapy	X	X	X	х	X	X	
Administration of BI 836826		Х	X				
General safety laboratory parameters 	X	X	X	X	X	X	
Screening for Tumour Lysis Syndrome 		X	X	X	X		
Serum pregnancy test 	X	X					
CMV monitoring 	X	X				Х	
			1				
				İ			
							4
							-
Virology screening	x						
(HBV, HCV, HIV, CMV)							

End of treatment, performed 14 days (± 2 days) after the last administration of BI 836826 EOT:

CMV: Cytomegalovirus

Hepatitis B Virus HBV:

Hepatitis C Virus HCV:

HIV: Human Immunodeficiency Virus

\* the visit number follows the course number, i.e. visit 2 course 1 will read C1\_V2 and visit 2 course 2 will read C2\_V2 ...

\*\* the planned duration of a treatment course is 14 days

1 After informed consent, and review of in- and exclusion criteria, and before the first administration of the trial drug 3

For details refer to Section 5.2.3.1

Page 5 of 111

- 4 5
- Screening for tumour lysis syndrome in between safety laboratory assessments (Section 5.2.3.2) For women of childbearing potential only (please refer to Sections 3.3.3 (exclusion criterion 18) and 5.2.3.1) Quantitative CMV DNA PCR or pp65 antigen Section 5.2.3.3.2 6

Page 6 of 111

#### Flow Chart Courses 2 - 8

Trial Periods		Tre	atment**		ЕОТ	FU
Course *			2 - 8			
Visit *	1		2	3	ЕОТ	
Days	1	2	3 (+2)	8 (+2)		
12 lead-ECG					X	
Physical examination,	X				X	х
ECOG performance status						
Vital signs	X	X	X	X	X	X
Weight	X				X	X 1
Adverse events	X	X	X	X	X	x 
Concomitant therapy	X 89	X	X	X	X	x 
Disease / response assessment	x 				X	х
(blood, clinical)						
Administration of BI 836826	X					
Eligibility for further course	x 9					
General safety laboratory parameters 	X	X	X	X	X	Х
Screening for Tumour Lysis Syndrome 	X	X				
Serum pregnancy test 	X				X	
_CMV monitoring 	X			 	x	X
			-			
		1				▏▋
End of active trial treatment					x	┣ ┛ ───
Outcome (remission, progression, death)					X	X
Other therapy for CLL						X

EOT: End of treatment, performed 14 days (± 2 days) after the last administration of BI 836826 FU: Follow-up, starts after EOT, visits at least every 4 weeks until 6 months after EOT, details see Section 6.2.3.2

CMV:

Cytomegalovirus HBV: Hepatitis B Virus

HCV: Hepatitis C Virus

Human Immunodeficiency Virus HIV:

\* the visit number follows the course number, i.e. visit 2 course 1 will read C1 V2 and visit 2 course 2 will read C2 V2 ...

\*\* the planned duration of a treatment course is 14 days

- 1 For AE assessment during FU refer to Sections 5.2.1 and Section 6.2.3.2
- 2 Concomitant therapy during FU only in case indicated for treatment of an AE (Section 4.2.1).
- 3 For details refer to Section 5.2.3.1
- 4 Screening for tumour lysis syndrome in between safety laboratory assessments (Section 5.2.3.2)
- 5 For women of childbearing potential only (please refer to Sections 3.3.3 (exclusion criterion 18) and 5.2.3.1)
- Quantitative CMV DNA PCR or pp65 antigen (Section 5.2.3.3.2) 6

Boehringer Ingelheim BI Trial No.: 1270.1		04 Mar 2015	
	568809-08	Trial Protocol	Page 7 of 111
8	prior to starting treatmen	nent (peripheral blood, clinical) has to be perfo nt, and at day 1 of subsequent courses prior to t ed 1 day earlier to allow for a timely continuation reatment administration.	he next administration of BI
9			

If patients continue beyond cycle 8 in agreement with investigator and BI, the same assessments will be done as applicable for cycle 5-8.

[figure not shown]

**Trial Protocol** 

## **ABBREVIATIONS**

ADCC AE ALT ANC anti-HB anti-HBc	Antibody dependent cellular cytotoxicity Adverse Event Alanine amino transferase Absolute Neutrophil Count Hepatitis B surface antibody Hepatitis B core antibody
anti-HCV	Hepatitis C antibody
AP	Alkaline phosphatase
aPTT	Activated partial thromboplastin time
ASCT	Autologous stem cell transplant
AST	Aspartate amino transferase
BLQ	Below the lower limit of quantification
CA	Competent Authority
CD	Cluster of Differentiation
CDC CI	Complement dependent cytotoxicity Confidence Interval
CI	Confidence Interval
CLL	Chronic Lymphocytic Leukaemia
CML	Clinical Monitor Local
CMV	Cytomegalovirus
CR	Complete Remission
CRi CRA	Complete Remission with incomplete marrow recovery Clinical Research Associate
CRF	Case Report Form
CRO	Clinical Research Organisation
СТ	Computer tomography
CTCAE	Common Terminology Criteria for Adverse Events
CTMF	Clinical Trial Master File
CTP	Clinical Trial Protocol
CTR	Clinical Trial Report
DILI	Drug-Induced Liver Injury

DLT	Dose Limiting Toxicity
DSMB	Data Safatu Manitaring Board
eCRF	Data Safety Monitoring Board
ECG	Electronic Case Report Form Electrocardiogram
ECOG	Eastern Cooperative Oncology Group
EDC	Electronic Data Capture
EDC	Electionic Data Capture
EOT	End of active treatment
EudraCT	European Clinical Trials Database
FAS	Full Analysis Set
FDA	Food and Drug Administration
FFS	Failure free survival
GCP	Good Clinical Practice
G-CSF	Granulocyte colony stimulating factor
GFR	Glomerular filtration rate
НАНА	Human anti-human antibodies
HBsAg	Hepatitis B surface antigen
HBV	Hepatitis B Virus
HCV	Hepatitis C Virus
HIV	Human immunodeficiency virus
IB	Investigator's Brochure
ICH	International Conference on Harmonization
IEC	Independent Ethics Committee
INR	International normalised ratio
IRB	Institutional Review Board
ISF	Investigator Site File
IUD	Intrauterine device
i.v.	intravenous
IWCLL	International Workshop on Chronic Lymphocytic Leukemia
LDH	Lactate dehydrogenase
MTD	Maximum Tolerated Dose
MedDRA	Medical Dictionary for Drug Regulatory Activities
NBE	New biological entity
NC	Not calculated
NHL	Non-Hodgkin-Lymphome
NOA	Not analyzed
OBD	Optimal Biological Dose
OPU	Operative Unit

PCR	Polymerase chain reaction
PD	Progressive disease
PFS	Progession free survival
PLT	Platelets
p.o.	per os (oral)
PR	Partial remission
PT	Prothrombin time
RBC	Red blood cell count
SAE	Serious Adverse Event
S.C.	subcutaneous
SD	Stable disease
SDV	Source data verification
SMIP	Small modular immuno pharmaceutical
SOP	Standard Operating Procedure
SPC	Summary of Product Characteristics
SUSAR	Suspected unexpected serious adverse reaction
TCM	Trial Clinical Monitor
TDMAP	Trial Data Management and Analysis Plan
TLS	Tumour lysis syndrome
TMM	Team Member Medicine
TMW	Trial Medical Writer
TSAP	Trial Statistical Analysis Plan
10/11	
WBC	White blood cell count
WHO	World Health Organisation
	() one needed of Ballowion

## **1. INTRODUCTION**

## 1.1 MEDICAL BACKGROUND

Chronic lymphocytic leukaemia (CLL) is the most common form of leukaemia in Europe and North America, accounting for approximately one third of all leukemias in these regions, with an estimated annual age-adjusted incidence of 3–5 per 100 000 persons. The disease is diagnosed most commonly in the elderly, with the median age at diagnosis of 65 to 70 years. CLL is characterized by the accumulation of non-proliferating, mature-appearing, monoclonal B-lymphocytes in the blood, bone marrow and lymphatic organs. Commonly used staging systems, e.g. the modified Rai- or the Binet-System, classify patients in three prognostic groups as low, intermediate or high risk.

CLL is considered incurable with standard therapy. Despite a high response rate of a first line therapy with rituximab, fludarabine and cyclophosphamide, most patients will eventually experience disease progression. After subsequent relapses treatment options become increasingly limited. This is particularly true in patients refractory to fludarabine, who have limited response to salvage therapy and poor survival (R10-4432).

As of today, three monoclonal antibodies have received a marketing authorisation by regulatory authorities for the treatment of relapsed or refractory CLL: Rituximab and ofatumumab (targeting CD20) and alemtuzumab (targeting CD52).

Rituximab has limited activity as monotherapy in CLL, however is effective in combination with cytotoxic chemotherapy. Rituximab is currently introduced into first-line treatment in combination with fludarabine containing regimens and it is not clear which patients should be re-exposed to rituximab for treatment of relapsed disease.

Of a tumumab is indicated for treatment of fludarabine and alemtuzumab refractory CLL and may be a treatment option for patients relapsing after rituximab containing regimens. Subgroup analyses in a limited number of patients have shown that treatment with Of a tumumab results in similar response rates in patients who had received prior rituximab containing regimens compared to those who have not. (R10-4435).

Treatment with alemtuzumab is effective in patients with unfavourable prognostic markers such as 17p deletion, 11p deletion, unmutated VH (R10-4434), however it has limited efficacy in patients with bulky nodal disease (R10-4433). Due to the ubiquitous expression of CD52 on lymphocytes and monocytes, alemtuzumab causes significant haematological adverse events and infectious complications. However, infectious complications are manageable with adequate antibiotic prophylaxis and treatment, and careful monitoring for CMV reactivation and other potential infections (R10-4430). Alemtuzumab has clinical activity in relapsed patients with del(17p13), who are resistant to most standard therapies. While only 5% of CLL patients have del(17p13) at diagnosis, up to half of patients acquire this abnormality as their disease progresses over time (R10-4505).

Boehringer Ingelheim		04 Mar 2015
BI Trial No.: 1270.1		
c01568809-08	Trial Protocol	Page 17 of 111

To broaden the spectrum of treatment options for subsequent relapses of this chronic disease, there is a high need to develop novel treatments targeting CLL-related antigens and pathways.

## **1.2 DRUG PROFILE**

BI 836826 is a antibody of the IgG1 isotype, directed against human CD37.

CD37, a member of the tetraspanin superfamily, is a glycosylated cell surface protein which is predominantly expressed on B-cells, with highest expression levels on mature peripheral blood B-cells. The majority of malignant cells in patients with B-NHL and CLL express the CD37 antigen (R08-2979, R08-2943, R08-2981, R08-2945, R08-2942).

The physiological function of CD37 in humans remains unknown (R08-2979, R08-2946). Mice deficient for CD37 display no changes in development and cellular composition of lymphoid organs but have reduced levels of IgG1 and attenuated T-cell mediated immune reactions (R09-5412). Studies with CD37-/- T-cells suggest a role for CD37 in T-cell proliferation and regulation of IgA response (R09-4740, R09-5414).

D 10 1111

Page 18 of 111

Page 19 of 111

## 2. RATIONALE, OBJECTIVES, AND BENEFIT - RISK ASSESSMENT

## 2.1 RATIONALE FOR PERFORMING THE TRIAL

CD37 is predominantly expressed on B-cells, with highest expression levels on mature peripheral blood B- cells, reduced levels on plasma cells and low levels on monocytes, T-cells, macrophages, and granulocytes (R08-2979, R09-4740, R09-4739). The physiological function of CD37 in humans remains unknown (R08-2979, R08-2946). However, mice deficient for CD37 display no changes in development and cellular composition of lymphoid organs but have reduced levels of IgG1 and attenuated T-cell mediated immune reactions (R09-5412). The majority of malignant cells in patients with B-NHL including CLL express the CD37 antigen (R08-2979, R08-2943, R08-2981, R08-2945, R08-2942). Therefore, targeting CD37 in malignancies of B-cell origin may offer a new treatment option.

Clinical data of advanced B-NHL patients who were treated with the fully murine CD37 antibody MB-1 are published (R10-2734, R10-2735). In these trials, administration of a radio-immunoconjugate of MB-1 was safe, led to fast and specific B-cell reduction, a low degree of T-cell reduction and induced tumour shrinkage in advanced B-NHL patients already with tracer doses of the attached isotope.

The anti-CD37 small modular immuno-pharmaceutical (SMIP) TRU-016 was well tolerated in an ongoing phase I trial at doses up to 10 mg/kg in patients with CLL, with predominantly haematological dose limiting toxicities (R10-2733).

The clinical experience with MB-1 and TRU-016 supports the assumption that targeting CD37 in the human leads to lymphocyte reduction and consecutive lymph node shrinkage with an acceptable side effect profile.

This trial will be the first administration of BI 836826 in humans.

## 2.2 TRIAL OBJECTIVES

The primary objective of this trial is to determine the MTD of BI 836826. As BI 836826 is a new biological entity (NBE) and the MTD may not be reached, an optimal biological dose (OBD) may be defined instead, presuming pharmacokinetic or pharmacodynamic markers or clinical response parameters will indicate that BI 836826 exerts a relevant biological effect, e.g. a relevant reduction of B-cells, at a dose level with a low probability of toxicity. Secondary objectives are to document the safety and tolerability of BI 836826,

and to evaluate parameters of efficacy.

## 2.3 BENEFIT - RISK ASSESSMENT

Although considerable progress has been achieved in understanding the aetiology and biologic behaviour of CLL and the development of more effective treatment regimens, most patients with advanced or refractory CLL may eventually not be amenable to established forms of treatment. In particular, patients with resistant disease, relapse after fludarabine and

Boehringer Ingelheim
BI Trial No.: 1270.1
c01568809-08

alkylating agent containing regimens, a short time to progression after the first treatment, and/or leukemia cells with del (17p) should be offered participation in clinical trials testing investigative agents according to published recommendations (R10-4429).

Targeting CD37 in this patient population may potentially offer a benefit to these patients, because cross-resistance with prior therapies is not to be expected.

BI 836826 is a monoclonal antibody which specifically targets CD37. In-vitro, BI 836826 was able to induce apoptosis of the target cells which resulted in depletion of B-cells from blood and lymphatic organs. In the clinical setting, these effects may potentially result in antitumour activity as a monotherapy, but also as in combination with other monoclonal antibodies or cytotoxic drugs in patients with Non-Hodgkin-Lymphoma (NHL) of B-cell origin including CLL.

BI 836826 has not previously been used in humans. CD37 is not expressed outside of the haematopoietic and lymphatic system.

Patients with CLL and active disease requiring treatment after at least two lines of therapy with limited or no standard treatment options may benefit from tumour cell reduction, tumour stabilization or improvement of tumour-related symptoms resulting from treatment with BI 836826. The potential benefit of therapy with BI 836826 is expected to outweigh the treatment-related risks.

## **3. DESCRIPTION OF DESIGN AND TRIAL POPULATION**

## 3.1 OVERALL TRIAL DESIGN AND PLAN

This trial will be performed in patients suffering from advanced or refractory chronic lymphocytic leukemia (CLL) who have failed two prior lines of therapy. It will be performed in an open, non-randomized, modified 3+3 design.

Initially, patients will be treated at escalating dose levels to determine the MTD.

Single patient cohorts will be treated until either a drug-related adverse event of CTCAE grade 2 or higher occurs, or until a relevant pharmacodynamic effect (i.e. a reduction of Blymphocytes in the blood by more than 50%) is documented in a patient during the first treatment course. As soon as one of these criteria applies, cohorts will be expanded to three to six patients according to a standard 3+3 design, following a fixed dose escalation design with dose de-escalation steps (R04-0569). The dose level will be escalated with each new cohort until at least one out of three patients of a cohort experiences a DLT (for definition see 5.2.1.1). If exactly one out of the three patients of the cohort experiences a DLT, three additional patients will be treated at the same dose level. If none of the three additional patients experiences a DLT, then the dose escalation will be continued by treating the next cohort of three patients at the next higher dose level. If at least two out of up to six patients at a dose level experience a DLT, the MTD has been exceeded and the dose will be deescalated until a dose level is reached in which at most one DLT out of six patients is observed (R01-0028). The MTD is defined as the dose of BI 836826 that is one dose cohort below the dose at which two or more out of six patients experienced DLT. At the maximum tolerated dose, no more than one patient out of six patients may experience DLT, i.e., the MTD is defined as the highest dose studied for which the incidence of dose-limiting toxicity is no more than 17% (i.e., 1/6 patients) during the first course.

During the dose escalation phase, each patient will receive up to 4 repeated treatment courses. In patients who show an unequivocal clinical benefit after 4 courses of treatment, the number of treatment courses on the same dose level may be increased to 8 in agreement between investigator and Clinical Monitor of Boehringer Ingelheim. Depending on the observed adverse events, dose cohorts on escalating dose levels will be enrolled until the MTD has been defined by the occurrence of dose limiting toxicities (DLT).

After definition of the MTD, it is planned to enroll an expansion cohort of 12-30 patients to better characterize the safety and possibly adapt the dose recommended for phase II prior to starting the next trials. Patients enrolled in the expansion cohort may receive up to 8 repeated treatment courses, provided that 4 courses are considered safe based on the available data on safety and pharmacokinetic parameters from patients treated during the dose escalation phase.

During the dose escalation phase, enrolment into the same dose cohort will be allowed the earliest 7 days after the first administration of the first dose to the previous patient in this dose cohort. Enrolment into the next higher dose cohort is allowed after the previous dose cohort was found to be safe for the initial application of the last patient in this cohort, i.e. at

Boehringer Ingelheim		04 Ma
BI Trial No.: 1270.1		
c01568809-08	Trial Protocol	Page 23

least 14 days after the first application of drug in this patient. Enrolment in this context refers to the day of administration of the first dose to a patient.

Once the MTD is defined, a dose for treatment of the expansion cohort will be determined, which will not exceed the MTD. In case the MTD will not be reached, an OBD may be defined instead. This dose will be discussed and agreed between Coordinating Investigator and the sponsor. The dose recommendation for the expansion cohort will be independently reviewed by the DSMB in the same way as outlined previously for the dose escalation phase of the trial. The Competent Authority will receive a summary of all safety findings observed by that time and the recommended dose for the expansion cohort. During treatment of the expansion cohort, new patients may be enrolled at any time.

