#### 3.3.4.2 Discontinuation of the trial by the sponsor

Boehringer Ingelheim reserves the right to discontinue the trial overall or at a particular trial site at any time for the following reasons:

- 1. Violation of GCP, the CTP, or the contract by a trial site or investigator, disturbing the appropriate conduct of the trial,
- 2. Emergence of any efficacy/safety information that could significantly affect continuation of the trial,
- 3. Failure to meet expected enrolment goals overall or at a particular trial site.

The investigator / the trial site will be reimbursed for reasonable expenses incurred in case of trial termination (except in case of the first reason).

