#### 4.1.3 Selection of doses in the trial

BI 836826 will be administered as a rate-controlled, intravenous infusion on day 1, 2 and possibly day 8 in course 1 and on day 1 in the subsequent courses.

A fixed dose of 1 mg BI 836826 per patient was determined to be the safe first in human starting dose for patients with an advanced haematological malignancy. The calculation of the safe starting dose of 1 mg in humans was based on data from studies in Cynomolgus monkeys and from ex vivo experiments with primary B-cells obtained from fresh blood samples of CLL patients. This dose is anticipated to represent a low pharmacologically active dose which may be capable to result in a detectable B-cell reduction in the peripheral blood of CLL patients. For details please refer to the Investigator's Brochure, Section 5.6.3 (U10-1892-01).

The dose is planned to be escalated in cohorts at pre-defined dose levels based on a multiplication factor of approximately 3 in the low dose range, and a factor of 2 at doses higher than 25 mg. The dose levels per treatment course are 1 mg, 3 mg, 9 mg, 25 mg, 50 mg, 100 mg, 200 mg ..., up to 1400 mg. At doses higher than 200 mg, the next dose cohort will be enrolled at a dose which is at maximum two times of the previous dose.

Every time a dose escalation is to be performed, the data of all previous dose cohorts will be reviewed and discussed between the Coordinating Investigator and the sponsor. The same data and the recommendation of the Sponsor and Coordinating investigator will be provided to the DSMB who will be asked to provide an independent assessment including a dose recommendation for the next cohort. As a result, lower dose increments than the predefined levels will be possible.

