#### 7.3 PLANNED ANALYSES

#### 7.3.1 **Primary analyses**

The primary objective for this study is the tolerability and safety of BI 836826 as reflected by the MTD (for a definition of MTD, please refer to Section 3.1). In order to identify the MTD, the number of DLTs at each dose level must be presented. For the analysis of tolerability and safety, please refer to Section 7.3.3.

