#### 7.6 DETERMINATION OF SAMPLE SIZE

Assuming 3 cohorts of 1 patient only, 3 cohorts of 3 patients (i.e. no patients with DLT at given level) and 3 cohorts of 6 patients (i.e. 1 DLT witnessed in first 3 patients so further 3 patients exposed with no DLTs), 30 patients will be necessary for the dose escalation part of this trial.

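### SAP 5.1 keeps the MTD definition that labels the highest dose studied as the MTD when no dose is exceeded, a case the protocol treats as MTD not reached

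*Protocol*

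**What the plan says.** Protocol 3.1 escalates in single-patient cohorts and then by 3+3. A dose is exceeded when at least two of up to six patients have a DLT. The section then defines the MTD twice. The first definition is "one dose cohort below the dose at which two or more out of six patients experienced DLT". The second, introduced by i.e., is the "highest dose studied for which the incidence of dose-limiting toxicity is no more than 17% (i.e., 1/6 patients) during the first course".

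The protocol also provides for the case where no MTD is found. Section 2.2 says "the MTD may not be reached, an optimal biological dose (OBD) may be defined instead", provided that a relevant biological effect is seen at a dose with a low probability of toxicity. Section 3.1 repeats it: "In case the MTD will not be reached, an OBD may be defined instead". The same section says that cohorts are enrolled until DLTs have defined the MTD. Escalation has a ceiling; the levels in Protocol 4.1.3 run "25 mg, 50 mg, 100 mg, 200 mg ..., up to 1400 mg".

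Protocol 7.3.1 adds no definition of its own. It describes tolerability and safety "as reflected by the MTD (for a definition of MTD, please refer to" Section 3.1.

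SAP 4.1 notes that the protocol defines no primary endpoint and makes the MTD, with the number of patients with DLTs, the primary endpoint through SAP 5.1. SAP 5.1 restates only the second definition. It says that an OBD might be defined in place of the MTD, but not when. SAP 7.4 describes how the MTD follows from first-course DLTs and gives no outcome for an MTD that is not reached.

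**The concern.** The first definition needs an exceeded dose and the second does not. If escalation ends with every cohort at one DLT or fewer, the first yields no MTD and the second yields the highest dose given. Escalation could end that way at the 1400 mg ceiling, or earlier if the sponsor stops the trial, for instance for "Failure to meet expected enrolment goals overall or at a particular trial site" (Protocol 3.3.4.2).

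Read literally, the second definition also leaves the protocol's not-reached clauses with nothing to do: any tested dose with at most 1/6 DLTs would produce an MTD, so the MTD could not go unreached for lack of toxicity. The protocol as a whole therefore points to the first definition, and SAP 5.1 carries the other.

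At stake is the headline result of a first-in-human trial. Reporting an MTD tells readers that an upper limit set by toxicity was located. Reporting that the MTD was not reached tells them that it was not. The same DLT table would support either label.

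**Working it through.** **Figures stated in the plan.** Protocol 7.6 assumes three cohorts of one, three of three and three of six: 3×1 + 3×3 + 3×6 = 30 patients, and 30 + 30 for expansion = 60. Both reproduce, and 1/6 = 16.7% matches the stated 17%. The six-patient cohorts are described as "3 cohorts of 6 patients (i.e. 1 DLT witnessed in first 3 patients so further 3 patients exposed with no DLTs", so the planning scenario contains no exceeded dose. It is a patient count, not a predicted end state.

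**The two definitions applied to the same data.** The 400 and 800 mg levels assume doubling above 200 mg. The DLT counts are examples.

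| Escalation data | First definition | Second definition (SAP 5.1) |
|---|---|---|
| 0/3 at every 3+3 level to 1400 mg | not reached | 1400 mg |
| 1/6 at 800 mg, 0/3 at 1400 mg | not reached | 1400 mg |
| Stopped at 200 mg with 0/3 | not reached | 200 mg |
| 1/6 at 400 mg, 2/6 at 800 mg | 400 mg | 400 mg |

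The definitions agree once a dose is exceeded and the dose below it has at most 1/6. They disagree in all three examples without an exceeded dose.

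**Cohort size.** The SAP wording sets no minimum, so 0/3 qualifies. The one-sided 95% exact upper limit for the DLT rate after 0/3 is 1 − 0.05^(1/3) = 63%. Protocol 3.1 speaks of at most one DLT in six at the MTD.

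**How often the case could arise.** A 3+3 level is passed with 0/3, or with 1/3 followed by 0/3. For DLT rate p:

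P(pass) = (1−p)³ + 3p(1−p)²·(1−p)³ = (1−p)³ + 3p(1−p)⁵

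At p = 0.10 this is 0.729 + 0.3×0.59049 = 0.906. For k levels at a flat rate, the chance that no dose is exceeded is P(pass)^k. The rates are assumptions, as are escalation to 1400 mg and no DLT in the single-patient cohorts.

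| p | P(pass) | 6 levels (from 50 mg) | 7 levels (from 25 mg) | 8 levels (from 9 mg) |
|---|---|---|---|---|
| 0.02 | 0.9954 | 97% | 97% | 96% |
| 0.05 | 0.9734 | 85% | 83% | 81% |
| 0.10 | 0.9061 | 55% | 50% | 45% |
| 0.15 | 0.8138 | 29% | 24% | 19% |
| 0.20 | 0.7086 | 13% | 9% | 6% |

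A rate that rises with dose is more realistic. Take seven levels with logit(p) linear in log dose, from 2% at 25 mg. The product of the P(pass) values is 78%, 48%, 24% or 10% when the rate at 1400 mg is 10%, 20%, 30% or 40%. With 20% at 1400 mg, it is 53% if the 25 mg rate is 1% and 36% if it is 5%.

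These are chances that the two definitions part company. They are not chances of a wrong label or a wrong dose.

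**The case against.** The strongest reply is that SAP 5.1 does not choose the MTD. SAP 7.8 says its tables summarise and document the data behind the selection. The selection itself follows the protocol's escalation rules, with review by the sponsor, the Coordinating Investigator and the DSMB. SAP 3 presents the SAP as an elaboration of the protocol and sends readers there for objectives and design, and SAP 4.1 lists no change to the MTD definition. Protocol 3.1 says that DLTs define the MTD. On this view the protocol still governs, and a report author who reads it will not call an untested ceiling the MTD. This stands, and it limits the point to the reported label.

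Two further replies stand in part. SAP 5.1 does mention the OBD, so the option survives; what is missing is the condition that triggers it. And parts of the SAP are not visible, including some of 7.8.1.1, so a condition could appear there. The point therefore rests on 5.1 and 7.4 as they can be read.

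A reader might infer that the trial could escalate wrongly, give patients an unsafe dose, or choose the wrong expansion dose. The documents do not support that. The expansion dose is agreed separately, reviewed by the DSMB and sent to the Competent Authority, and DLTs are tabulated by dose whatever the label. Nor did the SAP invent its wording: it kept one of two sentences already in Protocol 3.1.

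**Conclusion.** The point holds as a minor correction to the primary-endpoint definition. Protocol 3.1 equates two definitions that differ whenever no dose has two or more DLTs, and SAP 5.1 keeps the one that conflicts with the protocol's own provision for that case. This is more than missing detail, because the stated rule, taken literally, gives the wrong headline result in a situation the protocol foresees twice.

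Its reach is narrow: the reported primary conclusion and nothing else. The conflict follows from the wording and needs no assumed rate. Its frequency does depend on assumed rates, and the flat-rate range of 6% to 97% shows only that the case is plausible.

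**What to change.** In SAP 5.1 and 7.4, keep the 17% incidence definition and add:

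*An MTD is declared only if a higher dose was exceeded (2 or more DLTs in up to six escalation-phase patients) and at least six evaluable patients were treated at the MTD dose with a DLT incidence of no more than 17% in the first course. If no dose was exceeded, report: MTD not reached; highest dose studied = X (DLTs/n); and apply the OBD route of Protocol 2.2 and 3.1.*

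The incidence wording should stay because the MTD evaluation set in SAP 6.3 is not limited to the escalation phase. A dose with six escalation and 30 expansion patients would hold 36, where a limit of one DLT in six patients is unclear but 17% still works (6/36 = 16.7%).

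The cost is a few sentences and one outcome line in the primary table, plus matching wording in Protocol 3.1 if it is still being amended. No patients, visits or data are added.
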